5.3 During your life, with how many people have you had sexual intercourse?

- a. 1 person
- b. 2 people
- c. 3 people
- d. 4 people
- e. 5 people
- f. 6 or more people

5.4 During the past month, how many people have you had sex with? \_\_\_\_\_ [# of people]

5.5 During the past month, how many TIMES have you had sex? \_\_\_\_\_ times

5.6 Of the times you had sex over the past month, how many TIMES was a condom used?  
\_\_\_\_\_ times

5.7 Of the times you had sex over the past month, how many TIMES did you use birth control other than a condom, like birth control pills or having a deprova shot?  
\_\_\_\_\_ times

Over the past month, did you drink alcohol or take any kind of drug and have sex? Yes No

5.9 Did you drink alcohol or use drugs before you had sexual intercourse the **last** time?

- a. I have never had sexual intercourse
- b. Yes
- c. No

5.10 The last time you had sexual intercourse, what one method did you or the person you had sex with use to prevent pregnancy? (Select only one response.)

- a. No method was used to prevent pregnancy
- b. Birth control pills
- c. Condoms
- d. An IUD (such as Mirena or ParaGard) or implant (such as Implanon or Nexplanon)
- e. A shot (such as Depo-Provera), patch (such as OrthoEvra), or birth control ring (such as NuvaRing)
- f. Withdrawal or some other method
- g. Not sure

5.11 How many times have you been pregnant or gotten someone pregnant?

- a. 0 times
- b. 1 time
- c. 2 or more times
- d. Not sure

5.12 Have you ever been tested for HIV, the virus that causes AIDS?

- a. Yes
- b. No
- c. Not sure

5.13 Have you ever been tested for other sexually transmitted diseases (STDs), such as genital herpes, chlamydia, syphilis, or genital warts?

- a. Yes
- b. No
- c. Not sure

5.14 Have you ever been told by a doctor or nurse that you had the HIV infection or any other sexually transmitted disease (STD)?

- a. Yes
- b. No
- c. Not sure

If yes, did you receive follow-up care? Yes No Not sure

5.15 Have you ever been tested for HCV (Hepatitis C)?

- a. Yes
- b. No

c. Not sure

5.16 Have you ever been told by a doctor or nurse that you had Hepatitis C?

- a. Yes
- b. No
- c. Not sure

If yes, did you receive follow-up care? Yes    No    Not sure

## Section 6: Substance Use Questions (secondary outcome variables)

These next questions are about alcohol and drug use.

6.1 How old were you when you tried any of the following for the first time?

Alcohol	I have never tried	8 years old or younger	9 or 10 years old	11 or 12 years old	13 or 14 years old	15 or 16 years old	17 years old or older
Marijuana (grass, pot, weed, or reefer)	I have never tried	8 years old or younger	9 or 10 years old	11 or 12 years old	13 or 14 years old	15 or 16 years old	17 years old or older
Meth (speed, crystal, crank, or ice)	I have never tried	8 years old or younger	9 or 10 years old	11 or 12 years old	13 or 14 years old	15 or 16 years old	17 years old or older
Cocaine (powder, crack, or freebase)	I have never tried	8 years old or younger	9 or 10 years old	11 or 12 years old	13 or 14 years old	15 or 16 years old	17 years old or older
Ecstasy (MOMA)	I have never tried	8 years old or younger	9 or 10 years old	11 or 12 years old	13 or 14 years old	15 or 16 years old	17 years old or older
Heroin (smack, junk, or diesel)	I have never tried	8 years old or younger	9 or 10 years old	11 or 12 years old	13 or 14 years old	15 or 16 years old	17 years old or older
Steroids (pills or shots without a doctor's prescription)	I have never tried	8 years old or younger	9 or 10 years old	11 or 12 years old	13 or 14 years old	15 or 16 years old	17 years old or older
Inhalants (sniff glue, breathe the contents of aerosol spray cans, or inhale any paints or sprays to get hiQh)	I have never tried	8 years old or younger	9 or 10 years old	11 or 12 years old	13 or 14 years old	15 or 16 years old	17 years old or older

6.2 During your life, how many times have you used any of the following:

Alcohol	0 times	1-2 times	3-9 times	10-19 times	20-39 times	40-99 times	100 or more times
Marijuana (grass, pot, weed, or reefer)	0 times	1-2 times	3-9 times	10-19 times	20-39 times	40-99 times	100 or more times
Meth (speed, crystal, crank, or ice)	0 times	1-2 times	3-9 times	10-19 times	20-39 times	40-99 times	100 or more times
Cocaine (powder, crack, or freebase)	0 times	1-2 times	3-9 times	10-19 times	20-39 times	40-99 times	100 or more times
Ecstasy (MOMA)	0 times	1-2 times	3-9 times	10-19 times	20-39 times	40-99 times	100 or more times
Heroin (smack, junk, or diesel)	0 times	1-2 times	3-9 times	10-19 times	20-39 times	40-99 times	100 or more times
Steroids (pills or shots without a doctor's prescription)	0 times	1-2 times	3-9 times	10-19 times	20-39 times	40-99 times	100 or more times
Inhalants (sniff glue, breathe the contents of aerosol spray cans, or inhale any paints or sprays to get high)	0 times	1-2 times	3-9 times	10-19 times	20-39 times	40-99 times	100 or more times

6.3 During the past 30 days, how many times did you use any of the following:

Alcohol	0 times	1 time	2 times	3 to 5 times	6 to 9 times	10 to 19 times	20 or more times
Marijuana (grass, pot, weed, or reefer)	0 times	1 time	2 times	3 to 5 times	6 to 9 times	10 to 19 times	20 or more times
Meth (speed, crystal, crank, or ice)	0 times	1 time	2 times	3 to 5 times	6 to 9 times	10 to 19 times	20 or more times
Cocaine (powder, crack, or freebase)	0 times	1 time	2 times	3 to 5 times	6 to 9 times	10 to 19 times	20 or more times
Ecstasy (MOMA)	0 times	1 time	2 times	3 to 5 times	6 to 9 times	10 to 19 times	20 or more times

Heroin (smack, junk, or diesel)	0 times	1 time	2 times	3 to 5 times	6 to 9 times	10 to 19 times	20 or more times
Steroids (pills or shots without a doctor's prescription)	0 times	1 time	2 times	3 to 5 times	6 to 9 times	10 to 19 times	20 or more times
Inhalants (sniff glue, breathe the contents of aerosol spray cans, or inhale any paints or sprays to get high)	0 times	1 time	2 times	3 to 5 times	6 to 9 times	10 to 19 times	20 or more times

6.4 During the past 30 days, on how many days did you have 5 or more drinks of alcohol in a row—that is, within a couple of hours?

- a. 0 days
- b. 1 day
- c. 2 days
- d. 3 to 5 days
- e. 6 to 9 days
- f. 10 to 19 days
- g. 20 or more days

6.5 During your life, how many times have you used a needle to inject any illegal drug into your body?

- a. 0 times
- b. 1 time
- c. 2 or more times

## **SECTION 7: BELIEFS ABOUT PREGNANCY (Other Variables)**

These questions are about your beliefs about pregnancy.

7.1. How old do you think a woman should be when she has her first child?

- a.       YEARS OLD
- b. I don't know.

7.2. How old do you think a man should be when he has his first child?

- a.       YEARS OLD
- b. I don't know.

7.3. If you or your partner/boyfriend/girlfriend had a child in the next year, please tell us how having a child would affect you. (Even if you don't have a partner right now, tell us what you think you would do if this happened.)

- a. It would interfere with my relationship with my partner.
  - i. Disagree
  - ii. Neither agree nor disagree
  - iii. Agree

- b. It would take away my freedom.
  - i. Disagree
  - ii. Neither agree nor disagree
  - iii. Agree
- c. It would interfere with my plans.
  - i. Disagree
  - ii. Neither agree nor disagree
  - iii. Agree
- d. It would be a real problem.
  - i. Disagree
  - ii. Neither agree nor disagree
  - iii. Agree
- e. It would fit in with my plans.
  - i. Disagree
  - ii. Neither agree nor disagree
  - iii. Agree
- f. My family would be upset or disappointed.
  - i. Disagree
  - ii. Neither agree nor disagree
  - iii. Agree
- g. My family would kick me out.
  - i. Disagree
  - ii. Neither agree nor disagree
  - iii. Agree
- h. It would give my life direction.
  - i. Disagree
  - ii. Neither agree nor disagree
  - iii. Agree
- i. It would make it difficult to get or keep a job.
  - i. Disagree
  - ii. Neither agree nor disagree
  - iii. Agree
- j. I would consider it a great gift.
  - i. Disagree
  - ii. Neither agree nor disagree
  - iii. Agree
- k. It would encourage me to keep my job or look for a better job.
  - i. Disagree
  - ii. Neither agree nor disagree
  - iii. Agree
- l. My family would support me.
  - i. Disagree
  - ii. Neither agree nor disagree
  - iii. Agree
- m. It would make it difficult to stay in school.

- i. Disagree
- ii. Neither agree nor disagree
- iii. Agree

7.4. If you or your partner got pregnant within the next year or are currently expecting a child, how likely do you think it is that you would do any of the following things? (Even if you don't have a partner right now, tell us what you think you would do if this happened.)

I WOULD ...

- a. Raise the baby.
  - i. Not at all likely
  - ii. Not very likely
  - iii. Somewhat likely
  - iv. Very likely
- b. Get married or stay married.
  - i. Not at all likely
  - ii. Not very likely
  - iii. Somewhat likely
  - iv. Very likely
- c. Put the baby up for adoption.
  - i. Not at all likely
  - ii. Not very likely
  - iii. Somewhat likely
  - iv. Very likely
- d. Give the child to a relative to raise.
  - i. Not at all likely
  - ii. Not very likely
  - iii. Somewhat likely
  - iv. Very likely

## **SECTION 8: BELIEFS ABOUT BIRTH CONTROL METHODS, STIs, & HCV (Other Variables)**

These next questions are about your beliefs about birth control and sexually transmitted diseases.

8.1 I believe that ...

- a. Used correctly, most birth control methods will lower the chances a woman will get pregnant.
  - i. Disagree
  - ii. Neither Disagree nor Agree
  - iii. Agree
- b. Talking about birth control methods will make your partner uncomfortable.
  - i. Disagree
  - ii. Neither Disagree nor Agree
  - iii. Agree
- c. Using some birth control methods can be dangerous to a woman's health.
  - i. Disagree
  - ii. Neither Disagree nor Agree
  - iii. Agree
- d. Talking about birth control methods with your partner will bring the two of you a lot closer.

- i. Disagree
- ii. Neither Disagree nor Agree
- iii. Agree

e. It is hard for Indian women to accept using birth control methods because at times in the past the federal government forced it on them.

- i. Disagree
- ii. Neither Disagree nor Agree
- iii. Agree

f. Some birth control methods are too difficult to use correctly.

- i. Disagree
- ii. Neither Disagree nor Agree
- iii. Agree

g. Most of my friends and same-age relatives who have sexual intercourse use some type of birth control method.

- i. Disagree
- ii. Neither Disagree nor Agree
- iii. Agree

h. My friends and same-age relatives encourage me to use some type of birth control method every time I have sexual intercourse.

- i. Disagree
- ii. Neither Disagree nor Agree
- iii. Agree

## 8.2. I believe that ...

a. My parents and most of my older relatives have talked with me about abstinence (not having sexual intercourse) as a method of birth control.

- i. Disagree
- ii. Neither Disagree nor Agree
- iii. Agree

b. My parents and most of my older relatives have talked with me about the importance of using some type of birth control method.

- i. Disagree
- ii. Neither Disagree nor Agree
- iii. Agree

c. I will insist on using a condom with a new sexual partner, even if my partner doesn't want to.

- i. Disagree
- ii. Neither Disagree nor Agree
- iii. Agree

d. If I were going to have sex in the next year, I would use condoms.

- i. Disagree
- ii. Neither Disagree nor Agree
- iii. Agree

e. I would avoid using condoms if at all possible.

- i. Disagree
- ii. Neither Disagree nor Agree
- iii. Agree

- f. Using condoms makes sex feel unnatural.
  - i. Disagree
  - ii. Neither Disagree nor Agree
  - iii. Agree
- g. You feel closer to your partner when you don't use condoms.
  - i. Disagree
  - ii. Neither Disagree nor Agree
  - iii. Agree
- h. If I decided to have sexual intercourse with someone, I'm quite certain I could get my partner to agree to use condoms.
  - i. Disagree
  - ii. Neither Disagree nor Agree
  - iii. Agree
- i. If my partner wanted to use a condom, we could use one correctly.
  - i. Disagree
  - ii. Neither Disagree nor Agree
  - iii. Agree
- j. I would never talk to a sex partner about using condoms.
  - i. Disagree
  - ii. Neither Disagree nor Agree
  - iii. Agree

8.3 The next few questions are about Hepatitis C (HCV). Answer True or False.

a. HCV has no long-term effects on your health.....	True	False
b. It is possible to be vaccinated against HCV.....	True	False
c. People who have injected drugs are not at risk for HCV.....	True	False
d. HCV can be transmitted by tattooing and body piercing.....	True	False
e. All people who have HCV can be cured.....	True	False
f. HCV can be transmitted by sharing razors or toothbrushes.....	True	False
g. A person can get HCV by sharing a needle and syringe with someone when injecting drugs.....	True	False
h. A woman can get HCV through having sex with a man.....	True	False
i. A person can get HCV from mosquitos.....	True	False
j. Someone who looks very healthy can pass on HCV.....	True	False

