### **6.3.2. List of Data Source Materials and Measures (Table 2 below).**

**Student Survey:** To assess students' participation in N/E, we draw from several existing measurements that have been implemented and validated in research studies with AI youth. Primary outcome measure: Condom use will measure frequency of condom use relative to frequency of sex during sexual intercourse using questions derived from the Risk Behavior Assessment. Secondary outcome measures: These will include the number of sex partners; age of onset of sexual intercourse; frequency of sexual intercourse; pregnancy history; frequency and type of birth control used during sexual intercourse relative to the frequency of sexual intercourse; and frequency and types of substance use (cigarettes, marijuana, alcohol, and methamphetamine). Tertiary outcome measures: Parent/legal guardian communication is measured by the frequency and types of SRH topics that parent/legal guardian and child discussed. Cultural identity is measured using two established measurements: One measure assesses the extent to which a student identifies with his or her American Indian culture and feels cultural pride, and the other measure assesses frequency and type of participation in cultural activities. Access to SRH services is measured by frequency and type of SRH service used (ever been tested for STIs and follow-up, ever been tested for HIV and follow-up, ever been tested for HCV and follow-up, ever been pregnant/gotten someone pregnant and follow-up). Other variables to be measured in N/E that assess attitudes, intentions, skills, and mental health are: Motivation to avoid STIs, HIV, HCV, and pregnancy, as measured by asking students how important it is to them to keep themselves (or someone else) from getting an STI, HIV, and HCV, and how important it is to them to keep from getting pregnant or getting someone pregnant. Intention to use condoms and/or birth control is measured by asking students how likely it is they will use condoms and/or birth control the next time they have sexual intercourse. Intention to abstain from sex is measured by asking students how likely it is that they will not participate in sexual intercourse. Condom and birth control use self-efficacy is measured by assessing confidence in one's ability to use condoms and birth control. Refusal skills regarding sex are assessed by how strongly students believe they can say no to sex. Knowledge about STIs, HIV, HCV, pregnancy, and healthy relationship characteristics are measured using true/false/don't know questions. Mental health is assessed using two established measures: One measure assesses depression using the C-ESD, and the other measurement assesses exposures to stressful life events by assessing lifetime occurrences of a series of negative events. Standard demographic measures in the student survey are age, gender, sexual orientation, school, and highest grade completed.

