**Table 2. NIE Measures.**

**Table 2. N/E Measures.**

Data Collection Instruments and Measures	Data Collection: Baseline & Months				Description of Measures Number of Items; Scale Anchors; Benchmark Values	
	Base	3	9	12		
Student Survey						
Primary Outcome Variable						
Proportion of condom use during sexual intercourse (SI)	X	X	X	X	2 items; number of times condom used relative to number of times had SI	
Secondary Outcome Variables						
Age of onset of sexual intercourse	X	X	X	X	2 items; ever had SI & age at first SI	
Number of sex partners	X	X	X	X	2 items; lifetime & past-month sex partners	
Frequency of sexual intercourse	X	X	X	X	1 item; frequency of SI in past month	
Pregnancy history	X	X	X	X	1 item; number of pregnancies	
Type & frequency of birth control (BC) during sexual intercourse	X	X	X	X	3 items; type of BC use and number of times BC used during SI	
Type & frequency of substance use (SU) during sexual intercourse	X	X	X	X	1 item measures SU with SI; 5 items measure lifetime and past month SU	
Tertiary Outcome Variables						
Type & frequency of parent/legal guardian-child SRH communication	X	X	X	X	24 items Likert scale; higher score = higher communication	
Cultural identity & participation in cultural activities	X	X	X	X	3 items cultural identity ( $\alpha = .75$ ); 2 items cultural activities engagement ( $\alpha = .46$ )	
Type & frequency of SRH services	X	X	X	X	9 items; frequency, type, and follow-up of SRH services used	
Other Variables						
Motivation to avoid STIs, HIV, HCV, & pregnancy	X	X	X	X	Up to 9 items; 1 (very true) to 5 (very untrue); 1 = more positive attitude/motivation	
Condom & birth control use intention & self-efficacy	X	X	X	X	4 items per intention; 1 (very true) to 5 (very untrue); 1 = higher intention; 6 self-efficacy items; 1 (very easy) to 4 (very hard); 1 = high self-efficacy	
Abstinence	X	X	X	X	3 items; 1 (strongly disagree) to 4 (strongly agree); 4 = more supportive of teen abstinence	
Refusal skills regarding sex	X	X	X	X	7 items; 1 (I definitely can say no) to 5 (I definitely can't); 1 = stronger refusal skills	
Knowledge of STIs, HIV, HCV, pregnancy, & health relationships	X	X	X	X	Range of 4 to 10 items per topic; True/False/DK; Average proportion of questions correct	
Depression (CES-D) & exposure to stressful life events	X	X	X	X	CES-D — 7 items ( $\alpha = .80$ ); Life Events — 24 items; Yes/No; number of events observed	
Student Demographics						

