## 6.4 Potential Risks

There may be minor risks to agreeing to participate in N/E. Student and parent/legal guardian participants may be asked some questions that make them feel uncomfortable, sad, or confused (e.g., questions about sexual risk behaviors). For participants in the systems-level component of the study that evaluates the enhancement of the coordination of SRH services, we anticipate low to no risks, since none of the data being collected will be of a personal nature. For Aim 3, which uses focus groups as one method of data collection to evaluate the fidelity and acceptability of N/E, we also anticipate low to no risk, since none of the data being collected will be of a personal nature. All study participants will be informed that they may choose to stop their participation in N/E at any time or decline to answer a particular question asked of them on a data collection instrument or during a data collection process. We will inform study participants that the study is voluntary and that they can withdraw from the study, by stating that they want to do so, at any time over the course of the study.

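### Item 8.3 offers only True/False for the ten HCV knowledge items although the plan specifies True/False/Don't know; guessing raises the expected floor to about 50% and attenuates measured gains, by half under random 50:50 guessing and by less in several other plausible cases

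*Combined protocol and SAP*

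**What the plan says.** Section 6.3.2 describes the student survey: "Knowledge about STIs, HIV, HCV, pregnancy, and healthy relationship characteristics are measured using true/false/don't know questions". Table 2 gives the format and the score: "Range of 4 to 10 items per topic; True/False/DK; Average proportion of questions correct". Both place knowledge among the other variables, measured at baseline and at 3, 9 and 12 months.

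The instrument differs. In Section 8 of the student survey, item 8.3 opens with "The next few questions are about Hepatitis C (HCV). Answer True or False". Each of the ten statements, a to j, is followed by True and False and nothing else. In the same survey, item 10.1 (healthy relationships) prints both a Don't Know and a refusal option.

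Section 6.4 lets a participant "decline to answer a particular question asked of them on a data collection instrument". The plan gives no guessing correction and no scoring rule for blank items on this scale.

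**The concern.** The instruction itself limits the answer to two choices, so the gap is not a column lost in reading the PDF. The plan and the instrument disagree on the response format of a scale that Table 2 schedules at all four surveys.

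The format matters because the score is a proportion correct. A student who does not know an answer scores nothing by ticking Don't know, but has about an even chance of a point by guessing between two options. Guessing lifts the score most where knowledge is lowest, and so shrinks the change that a curriculum is meant to produce, from not knowing to knowing. HCV is a named prevention target, with content in Native Stand session 12 and Native Voices session 3, and item 8.3 is the only HCV knowledge measure in the survey as published. Its level also cannot be read beside item 10.1, which has a Don't Know option and hence a different floor.

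**Working it through.** The documents state no baseline level, effect size, SD or power for HCV knowledge, so there is no figure of the plan to reproduce. The sample size does not use it: 292 x 1.3273 / 0.85 = 455.97, the stated 456, rests on condom use.

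**Inputs.** From the documents: ten items, two printed options, score = proportion correct. Assumed: chance g that a guess is right (0.5, range 0.3 to 0.7), share d of uninformed students who would tick Don't know (1, range 0 to 1), and an illustrative true gain from 0.40 to 0.60.

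**Model per item.** Let k be the share who know, m the share who are misinformed and answer wrongly, and u = 1 - k - m the share who are uninformed.

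- True/False: expected score = k + g x u
- True/False/Don't know, with Don't know scored as not correct: expected score = k + g x (1 - d) x u

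**Pure 50:50 guessing (m = 0, g = 0.5, d = 1).** The True/False score is 0.5 + 0.5k.

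| True knowledge | 0 | 0.2 | 0.4 | 0.6 | 0.8 | 1.0 |
|---|---|---|---|---|---|---|
| True/False/Don't know | 0 | 0.2 | 0.4 | 0.6 | 0.8 | 1.0 |
| True/False | 0.50 | 0.60 | 0.70 | 0.80 | 0.90 | 1.00 |

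A true gain of 0.20 is scored as 0.80 - 0.70 = 0.10, a ratio of 0.50.

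**Changing one assumption at a time**, for the same true gain of 0.20:

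| Change | Gain seen with True/False | Ratio |
|---|---|---|
| Half the gain from misinformed students | 0.20 - 0.5 x 0.10 = 0.15 | 0.75 of true gain |
| All the gain from misinformed students | 0.20 | 1.00 of true gain |
| g = 0.3 | 0.7 x 0.20 = 0.14 | 0.70 of true gain |
| g = 0.7 | 0.3 x 0.20 = 0.06 | 0.30 of true gain |
| d = 0.5 | 0.10, against 0.15 in the Don't know format | 0.67 of the Don't know format |
| 25% or 50% of uninformed students skip, blank = not correct | 0.125 or 0.15 | 0.63 or 0.75 of true gain |
| Same skipping, blanks dropped from the denominator | 0.098 or 0.089 | 0.49 or 0.45 of true gain |

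Skipping therefore softens the loss only if blanks are scored as not correct. If blanks are dropped, the loss is slightly above half.

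**In SD units.** Take the variance of a ten-item score with mean p and between-student SD s as (p(1 - p) - s²)/10 + s², averaged over the two time points. Under pure guessing, True/False halves s.

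- s = 0: 0.20/√0.024 = 1.29 against 0.10/√0.0185 = 0.74, ratio 0.57
- s = 0.20: 0.20/√0.060 = 0.82 against 0.10/√0.0275 = 0.60, ratio 0.74

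**What a guessing correction does.** With g = 0.5, 2 x (proportion correct) - 1 = 2(k + 0.5u) - 1 = k - m. It recovers k when nobody is misinformed. It is linear, so it doubles the mean change and the SD together and leaves the test statistic unchanged.

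**What a change of format after baseline does.** True knowledge of 0.40 scored as True/False reads 0.70. True knowledge of 0.60 scored with Don't know reads 0.60. A real rise of 0.20 would appear as a fall of 0.10.

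**The case against.** The best case on the other side is that little depends on this scale. Knowledge is an other variable. It is absent from hypotheses H1 to H3, from the outcomes in the registration receipt, and from the mixed-model section, which covers primary, secondary and tertiary outcomes. That stands, and it sets the rank of the point.

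It can also be said that nobody is forced to answer, since Section 6.4 lets a student decline any question. That is fair, but a skipped item is not a Don't know answer, and without a rule for blanks its effect on the score is undefined.

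Some items, such as transmission by mosquitoes or the existence of a vaccine, may draw confident wrong answers rather than guesses. That is plausible, and gains from such students are measured in full.

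Finally, Section 6.3.2 and Table 2 do not say outright that Don't know scores as not correct, which is inferred from the proportion-correct score. Nor do they plan to average HCV knowledge with other topics, since Table 2 speaks of items per topic. The different floors are therefore a caution for reporting, not an error in a planned analysis. None of this removes the disagreement between plan and instrument.

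**Conclusion.** The mismatch is established by the text: Section 6.3.2 and Table 2 specify True/False/Don't know, and item 8.3 offers True/False. With random 50:50 guessing the expected floor is about 50% and a gain among uninformed students is seen at half its size. Across the assumed ranges the gain seen runs from about 30% to 100% of the true gain. In SD units, under pure guessing, the effect is 57% to 74% of its value in the Don't know format.

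Stronger readings are tempting but not supported:

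- A reader might infer that every gain is halved. That needs every unknown item to be a 50:50 guess, nobody misinformed, nobody skipping, and every uninformed student willing to use Don't know. The documents establish none of these.
- A reader might infer that scores are pulled toward 50%. In fact 50% is the expected floor for uninformed students; higher scores move toward 100%, and full knowledge is not lifted.
- A reader might turn the loss into a sample-size multiple, here 1/0.74² = 1.8 to 1/0.57² = 3.1. That rests on an assumed gain and SD and on independent students, whereas this is a five-school stepped wedge with no power claim for knowledge.
- A reader might infer harm to the main result. The primary outcome and the sample size do not use this scale.

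This is a minor point worth correcting.

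**What to change.** **If baseline has not been collected:** add a Don't know option to items 8.3 a-j and state that it is scored as not correct. The instrument then matches Section 6.3.2 and Table 2. The cost is one response option in REDCap.

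**If baseline was collected as True/False:** this looks the likelier case, because Section 4.1 schedules baseline for mid-March to June 2019 and the file holds review-board approvals from 2020. Then:

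- Keep True/False at all four surveys. Follow-up surveys come only after a school starts the intervention, so a new format would be confounded with exposure.
- Correct Section 6.3.2 and Table 2 to say that the HCV items are True/False.
- Report HCV knowledge separately from scales with a Don't know option.
- Score blanks by one fixed rule, stated in advance.
- Present levels and changes with the correction 2 x (proportion correct) - 1, beside the uncorrected score. State that it assumes 50:50 guessing, that it estimates k - m where students are misinformed, and that it rescales the estimate without restoring power.

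The cost is a few lines of text and one line of scoring. The precision lost to guessing is not recovered.
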